10.4 Monitoring Procedure

At the time the study is initiated, the principal monitor and/or co-monitors will thoroughly review the protocol and case report forms with the Investigators and their staff. During the course of the study, the principal monitor, the co-monitor or their designated deputies shall be available to discuss by telephone or other means, questions regarding adverse reactions, removal of subjects from trial, conduct of the study, etc.

At the time of each monitoring visit, the monitor will review the case report forms of each subject in the trial to make certain that data is reported in a timely fashion, that all items have been completed and that the data provided are accurate and obtained in the manner specified in the protocol. The subject's clinical records will be reviewed to confirm that the case report form data are consistent with the physician's clinical records. The monitor will verify the adherence to the procedures and schedule as defined in the protocol. The subject's clinical records will be reviewed to determine whether recording of adverse reactions or side effects has been omitted on the case report forms. If this is found to be so, then the case report forms will be returned to the Investigator and corrected to include this information.

At the time of the monitoring visit, it is the responsibility of the participating site to provide completed up-to-date case report forms, and to provide ready access to source documents.

10.5 Reporting and Recording of Data

In the US, federal regulations require that copies of case report forms be retained by the Investigator for a period of no less than two (2) years following either the approval of Biological License Application or the withdrawal of the Investigational New Drug Application. The Sponsor will advise the Investigator when the two-year period begins. Attention of the Investigator is drawn to the fact that he/she may be subject to a field audit by FDA or other regulatory inspectors to verify that the study is conducted in accordance with the requirements of the protocol, as well as in compliance with Good Clinical Practices.

All information required by the protocol is to be provided, or an explanation given for omissions. A monitor will verify the validity and completeness of the forms at each monitoring visit.

All data and information on the case report forms are to be neatly recorded in type or legibly printed in black ink for ease of duplication, interpretation and analysis before submission to the Sponsor designee. All corrections on the case report forms should be crossed out neatly and the new entry initialed and dated by the member of the Investigator's staff making the correction. Prior to forwarding the final case report forms, they should be reviewed for completeness, accuracy and legibility by the Investigator.

Copies of the completed case report forms will be provided by the Sponsor for retention by the Investigator.

10.6 Changes in Protocol

There will be no alterations or changes in this protocol without the written consent of the sponsor, jCyte.

10.7 Investigational Product and Label Codes

The investigational product is jCell. Frozen vials of jCell (hRPC) drug product are provided to the qualified dose preparation facility by [name] of the GMP Facility at UC Davis, where the cells were manufactured and are currently cryopreserved.

When a study subject has been scheduled for treatment, the qualified dose preparation site will prepare the patient dose according to a standard procedure. Frozen cells are thawed and cultured 40-48 hours prior to injection. Following successful culture and testing, 65 μ l of cell suspension containing 6 million human retinal progenitor cells suspended in clinical grade medium (BSS PLUS) will be provided by the dose preparation facility to the clinical site, on ice, with targeted administration to the patient within 4 hours of cell harvest. Patients will undergo topical anesthesia prior to injection of the cells.

16. REFERENCES	
17 APPENDICES	
APPENDIX A: PRESENTATION OF DATA AND F	PROGRAMMING SPECIFICATIONS 23
General Tables Listings Missing or Incomplete Dates (i.e., Adverse Events Standard Calculations	23 23 24 and Concomitant Medications)
APPENDIX B: LIST OF TABLES, LISTINGS, AND	FIGURES
Index of Section 14 Index of Section 16.2	
APPENDIX D: TABLE, FIGURE, LISTING LAYO	JTS
Appendix D1: Study-Specific Shells for Section 14 Appendix D2: Study-Specific Shells for Section 16	

LIST OF ABBREVIATIONS AND DEFINITIONS OF TERMS

Abbreviation	Definition
AE	adverse event
ATC	Anatomical Therapeutic Chemical
BCVA	Best Corrected Visual Acuity
BP	blood pressure
CIL	critical illumination level
CME	cystoid macular edema
CS	clinically significant
CSR	clinical study report
CST	Contrast Sensitivity Test
DRA	donor reactive antibodies
eCRF	electronic case report form
E-ETDRS	electronic visual acuity testing algorithm
EZ	ellipsoid zone
FST	full-field stimulus threshold test
ICH	International Council for Harmonisation of Technical Requirements
	for Pharmaceuticals for Human Use
IOP	intraocular pressure
ITT	intent-to-treat
IVT	intravitreal
jCell	Human Retinal Progenitor Cells
KVF	Kinetic Visual Fields
LED	light emitting diode
LLMT	Low Luminance Mobility Test
LOD	limit of detection
MedDRA	Medical Dictionary for Regulatory Activities
MSS	maximum step speed
NCS	not clinically significant
OCT	optical coherence tomography
OD	oculus dexter (right eye)
OS	oculus sinister (left eye)
PRA	panel reactive antibodies
PT	preferred term
PVD	posterior vitreous detachment
QC	quality control
RP	Retinitis Pigmentosa

Abbreviation	Definition
SAE	serious adverse event
SAP	statistical analysis plan
SD	standard deviation
SD-OCT	spectral domain optical coherence tomography
SF	spatial frequency
SOC	system organ class
TEAE	treatment-emergent adverse event
TLs	tables and listings
UBM	ultrasound biomicroscopy
VF	visual field
WHO	World Health Organization

1. INTRODUCTION

This document outlines the statistical methods to be implemented during the analyses of data collected within the scope of jCyte Inc. JC02-2 [A Phase 2 Study of the Safety of Repeat Intravitreal Injection of Human Retinal Progenitor Cells (jCell) in Adult Subjects with Retinitis Pigmentosa (RP)]. The purpose of this statistical analysis plan (SAP) is to provide specific guidelines for the statistical analyses. Any deviations from this plan will be documented in the clinical study report (CSR).

2. STUDY DOCUMENTS

The following study documents are used for the preparation of the SAP:

- Protocol, version 4.0, dated 12 April 2021
- Annotated electronic case report form (eCRF), version 2.1, dated 14 Jul 2021
- Data management plan, version 1, dated 20 Jan 2021

3. STUDY OBJECTIVES

3.1 Primary Objective

The primary objective of the study is to assess the safety of repeat injection of jCell.

3.2 Secondary Objective

The secondary objective of the study is to assess the impact of repeat injection of jCell on measures of visual function and functional vision over a 12 month period, including Best Corrected Visual Acuity (BCVA), Low Luminance Mobility Test (LLMT), Contrast Sensitivity Test (CST), and Kinetic Visual Fields (KVF).

The study protocol lists mobility (maze) as a secondary objective. The name of this test has since changed to Low Luminance Mobility Test and this name is used throughout this analysis plan.

4. STUDY DESIGN AND PLAN

This is a prospective, multicenter, single arm, Phase 2 study of jCell for the treatment of RP. Eligible subjects include those previously treated with jCell.

A group of 25-30 subjects who have participated in a prior jCell study will be eligible. A minimum of 18 months must have elapsed between the prior jCell treatment and treatment in this study and the subject must have completed the 12 month Follow-up visit from the prior study with a reasonable record of study compliance.

Study subjects will be screened for eligibility, informed consent obtained, and eligible subjects will receive a jCell injection in a previously treated eye of 6×10^6 jCell. Subjects who have previously had both eyes treated will only have one eye re-treated, preferably the eye with best visual acuity. Exceptions to this can be made by the study investigator taking into consideration medical conditions or other circumstances that may impact the choice of eyes for treatment. Subjects will be monitored closely following injection for 60 minutes prior to being released home on the day of treatment, based on intraocular pressure (IOP) <30mm Hg and vital signs returned to pre-injection. Following treatment, all subjects will be treated with ophthalmic corticosteroid eye drops to minimize any inflammation from injection for a minimum of seven days (including tapering schedule), or longer as if determined by the study investigator. Blood samples for antibody testing (panel reactive antibodies [PRA] and donor reactive antibodies [DRA]) will be collected at Baseline and at Month 1 and Month 6. Subjects will be followed at specified intervals for 12 months for evidence of safety and efficacy.

Subjects may be asked to undergo additional, optional testing at Baseline and specified time points to explore retinal sensitivity and the characteristics of the injected jCells during follow-up.

5. DETERMINATION OF SAMPLE SIZE

25-30 (depending upon availability) previously treated jCell subjects will be re-treated in one previously treated eye to assess safety of reinjection. If a subject has been previously treated with jCell in both eyes, the better seeing eye will be selected for re-treatment unless there are specific circumstances that make this not advisable, as judged by the study investigator. This is considered to be an adequate number of subjects to be able to judge whether the safety profile is consistent with that which has been seen previously with an initial treatment (received in protocols JC-01 and JC-02) or a fellow eye treatment (received in protocol JC-01E). This number assumes that there will be at least 25 previously treated subjects who desire a repeat treatment in a previously treated eye.

6. GENERAL ANALYSIS CONSIDERATIONS

The statistical analyses will be reported using summary tables and listings (TLs). The International Council for Harmonisation of Technical Requirements for Pharmaceuticals for Human Use (ICH) numbering convention will be used for all TLs.

Continuous variables will be summarized by presenting the number of observations, means, standard deviations (SDs), medians, minimums, and maximums.

Categorical variables will be summarized by presenting counts and percentages of subjects in corresponding categories. Percentages for missing values are omitted and do not account for the percent calculation of other categories. Percentages are based on the total category count excluding the missing category if not otherwise mentioned. In certain tables (e.g. adverse events [AEs]), the total number of subjects is used as the denominator. Footnotes will specify the percent basis in those cases.

All summary tables will be presented using the single jCell treatment group.

Treatment will be analyzed as actually performed rather than as planned. Any subjects who do not receive the full dose of study drug will be analyzed with those who do receive the full dose of study drug.

Individual subject data obtained from the eCRFs and any derived data will be presented by subject in data listings.

The analyses described in this plan are considered a priori, in that they have been defined prior to database lock.

Any analyses performed after database lock will be considered post hoc and exploratory. Post hoc analyses will be labeled as such on the output and identified in the CSR.

All analyses and tabulations will be performed using SAS[®] statistical software, version 9.4 or higher (SAS Institute Inc). Tables and listings will be presented in RTF format.

The process for SAS program validation and quality control (QC) for programs and outputs is documented in the Synteract working instruction "SAS Programming Quality Control".

7. NOTATION OF TREATMENT GROUPS AND VISITS

7.1 Notation of Treatment Groups

The following notation of the treatment group will be used throughout the report:

Notation Used Throughout all Tables and Listings

6.0 x 10⁶ jCell

7.2 Visit Terminology

The following notation of the visit terminology will be used throughout the report:

Visit	Notation Used Throughout all Tables and
	Listings
SCREENING	Screening
BASELINE	Baseline
DAY 0	Day 0
DAY 1	Day 1
DAY 7	Day 7
DAY 28	Day 28
MONTH 3	Month 3
MONTH 6	Month 6
MONTH 9	Month 9

MONTH 12	Month 12
EARLY TERMINATION	Early Termination

8. ANALYSIS POPULATIONS

- The intent-to-treat (ITT) population comprises all subjects who enroll in the study and who provide any post screening data.
- The safety population comprises all subjects who receive any study treatment.

For the purposes of this study the safety population will be used for efficacy and safety analyses.

9. DEMOGRAPHICS, BASELINE CHARACTERISTICS, AND STUDY MEDICATIONS

9.1 Subject Disposition

Subject disposition information will be summarized for all subjects. Summaries will include the number of subjects enrolled, in each analysis population, the number and percentage of subjects completing the study and the primary reason for discontinuation.

9.2 **Protocol Deviations**

Protocol deviations that could potentially affect the safety or efficacy conclusions of the study are captured during the study and periodically reviewed. The final determination of major protocol deviations will be done prior to database hard lock during the data review meeting.

A listing of all protocol deviations including the category (major or minor) will be presented.

9.3 Demographic and Baseline Characteristics

Demographic variables include: age of subject at time of informed consent (years), sex, ethnicity, race, and childbearing potential. Other baseline characteristics include treatment eye, medical history, ocular medical history, height and weight.

Descriptive statistics will be presented for age, height and weight. Frequency counts and percentages will be presented for sex, ethnicity, race and treatment eye. Demographic and baseline characteristics will be summarized for the safety population. Data on childbearing potential will be included in a data listing only.

9.4 Medical History

The verbatim term of the ocular medical history or medical history condition/event will be coded using the Medical Dictionary for Regulatory Activities (MedDRA), version 23.1.

Summary tables will be prepared, summarizing the incidence and percentages within each system organ class (SOC) and preferred term (PT), ordered by descending subject incidence for each SOC and PT. Subjects reporting more than incidence at each level of summarization will be

included only once for the subject count.

Data on ocular medical history and medical history will also be presented in data listings.

9.5 Prior and Concomitant Medications

Prior and concomitant medication verbatim terms in the eCRFs will be mapped to the World Health Organization (WHO) Anatomical Therapeutic Chemical (ATC) classification and preferred names using the WHODrug Global B3 format, Sep.1.2020 release.

Partial dates will be imputed. For details on imputation rules, refer to Appendix A: Presentation of Data and Programming Specifications. Imputed dates are only used for classification of a medication as a prior or concomitant medication; no other calculation, such as durations, will be performed.

Prior medications are defined as any medication with an (imputed) start date and (imputed) stop date before the date of study drug administration.

Concomitant medications are defined as any medication that was started before the date of study drug administration and with an (imputed) stop date on or after the date of study drug administration, or that are ongoing from Screening/Baseline, or that are taken on or after the date of study drug administration.

If the medication cannot be classified as a prior or concomitant medication, the medication will be considered concomitant.

Concomitant medications will be summarized by ATC class and preferred name. These summaries will present the number and percentage of subjects using each medication. Subjects may have more than one medication per ATC class and preferred name. At each level of subject summarization, a subject is counted once if they reported one or more medications at that level. Each summary will be ordered by descending subject count in the total column by ATC level and preferred name.

Separate tables will be prepared to summarize concomitant medications. A listing will be created containing all prior and concomitant medications and will contain a flag identifying whether a medication is prior or concomitant.

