5.3 Supportive Care/Prohibited Treatments

Subjects will receive supportive measures as determined by their needs and according to the accepted standards of care. All subjects will be treated with ophthalmic corticosteroid eye drops (prednisolone acetate ophthalmic suspension) to minimize any inflammation for 7 days starting on the day of injection, with a decision by the Study Investigator at the Day 7 visit regarding whether/when to taper the Predforte or to switch to a different medication. If extended beyond 7 days, the reason for longer treatment should be documented. Cyclogyl, one drop twice daily, may also be given to the treated eye for 7 days. Upon day 7 examination, the Investigator will determine whether the drop can be discontinued depending on the exam findings. The Cyclogyl will cause dilation of the affected eye. This may result in light sensitivity or a brief burning sensation after instillation of the drop, but should not be a significant burden for subjects. The prohibited treatments are any immunosuppressant other than topical steroids as noted above.

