7.1.4 Blood Samples for Antibody Testing

Blood samples will be collected for testing for Panel Reactive Antibodies (PRA) and Donor Reactive Antibodies (DRA) from subjects prior to treatment, at 4 weeks post-treatment, and at 6 months post-treatment. Details of preparation/shipping of samples will be provided separately.

7.1.5 **Ophthalmic AEs**

Procedures will be performed at scheduled intervals to specifically assess eye AEs that may not be detected by usual AE reporting and to try and visualize the injected cells. Please refer to the study procedure manual for details of all ophthalmologic assessment procedures.

Slit lamp and fundus exam - The binocular slit-lamp examination provides a stereoscopic magnified view of the eye structures in detail, enabling anatomical diagnoses to be made for a variety of eye conditions. This assessment will include detection of anterior chamber cell or flare; acute cataract development or progression in phakic patients, or vitreous haze. Fundus exam allows for inspection of the retina, the cellular graft, and detection of retinal detachment.

Optos photography - Optos photography includes a widefield dilated Optos photograph of the posterior segment with any cell cluster from the anterior vitreous visualized in the photo frame along with the posterior segment/fundus.

IOP - Intraocular pressure is measured with a tonometer as part of a comprehensive eye examination. Measured values of intraocular pressure are influenced by corneal thickness and rigidity

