13.1 Study Drug Administration

Treatment compliance will be assessed via direct observation by the study investigator who is responsible for study drug administration. The exact time of injection will be recorded on the eCRF.

Study drug administration responses will be tabulated according to questions asked in the eCRF, including whether the total dose was administered, whether there were any dose interruptions, whether there were any AEs observed, whether the subject's vital signs are comparable to pre-treatment of study drug injection, the subject's IOP measurement post-treatment of study drug injection and whether the subject was prescribed topical treatment after treatment of study drug injection.

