13.3.1.1 Slit Lamp

For eye structures of eyelids, eyelashes, conjunctiva, sclera, cornea, and iris, subjects will be tabulated by the categories of Normal, Abnormal not clinically significant (NCS), and Abnormal clinically significant (CS) at each time point, and percentages will be displayed. For anterior chamber flare, subjects will be tabulated by the flare grade and the categories of Abnormal NCS and Abnormal CS.

For syneresis, subjects will be tabulated as Not Obvious and Obvious. For posterior vitreous detachment (PVD), subjects will be tabulated as None, Partial and Complete. For lens status, subjects will be tabulated as Aphakic, Pseudophakic, and Phakic.

For cataract type, subjects will be tabulated as Nuclear, Cortical, Posterior Subcapsular and Other. Subjects will also be tabulated by cataract grades of trace, 1+, 2+, 3+ and 4+.

Slit lamp assessments will be summarized separately for each eye.

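### The concomitant-medication table cannot show prolonged, restarted or intensified use of the steroid drops every subject receives, and the slit lamp section names no row for anterior chamber cell

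*SAP*

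**What the plan says.** **Steroid course.** Protocol 5.3: "All subjects will be treated with ophthalmic corticosteroid eye drops (prednisolone acetate ophthalmic suspension) to minimize any inflammation for 7 days". The first drops are given on injection day. At the Day 7 visit the investigator decides "regarding whether/when to taper the Predforte or to switch to a different medication". The same section adds a record-keeping rule: "If extended beyond 7 days, the reason for longer treatment should be documented". The protocol synopsis and SAP 4 describe the course differently: at least seven days with the taper counted inside that period, and longer at the investigator's discretion.

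**Medication summary.** SAP 9.5 tabulates concomitant medications by ATC class and preferred name (Table 14.1.5.1). "These summaries will present the number and percentage of subjects using each medication", and a subject counts once at each level. A drug is concomitant if taken on or after the injection date, and also if it was "started before the date of study drug administration and with an (imputed) stop date on or after the date of study drug administration". Imputed dates may be used only to classify a drug as prior or concomitant, not to compute durations, and no duration from observed dates is planned. Listing 16.2.3.4 holds the individual records.

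**Other output on topical treatment.** SAP 13.1 tabulates "whether the subject was prescribed topical treatment after treatment of study drug injection".

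**Slit lamp.** Protocol 7.1.5: "This assessment will include detection of anterior chamber cell or flare; acute cataract development or progression in phakic patients, or vitreous haze". SAP 13.3.1.1: "For anterior chamber flare, subjects will be tabulated by the flare grade and the categories of Abnormal NCS and Abnormal CS". That section does not mention anterior chamber cell.

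**The concern.** The primary objective is the safety of a second injection of allogeneic cells into a previously treated eye, and intraocular inflammation is an obvious event to look for. All subjects receive steroid cover from the day of injection, so inflammation may be damped before it is reported as an adverse event. How long the cover continued, and whether it was restarted or increased, is then part of the safety result. The protocol treats it that way by asking for a reason when treatment is extended.

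The planned summaries do not use that information. When a drug is given to everyone, a count of subjects who ever used it carries no information. If longer courses were common, no summary table in the clinical study report would say so.

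**Working it through.** The plan gives no figure to reproduce. The sample size of 25 to 30 is set by availability (SAP 5), with no assumed event rate, margin or power. The check applies the SAP's counting rule to assumed steroid courses.

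**1. Counting rule.** Row value = subjects with at least one record at that level / N, with N = 25. Assume 8 subjects depart from a 7-day course of drug A. The 8 and the 60 days are illustrative.

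| Course | Class row | Drug A row | Drug B row |
|---|---|---|---|
| All 25: 7 days of A | 25/25 | 25/25 | none |
| 8 of 25 extended to 60 days of A | 25/25 | 25/25 | none |
| 8 of 25 restart or increase A | 25/25 | 25/25 | none |
| 8 of 25 switch to or add B (same class) | 25/25 | 25/25 | 8/25 = 32% |

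The first three lines are identical, and would be for any number from 0 to 25 in place of 8. The fourth differs by drug name, though without duration or reason.

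**2. What an extended-use row would show.** Percentage = k/N, with exact (Clopper-Pearson) 95% intervals. For k = 0 the upper limit is 1 − 0.025^(1/N). The values of k are assumptions.

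| k | N = 25 | N = 30 |
|---|---|---|
| 0 | 0% (0 to 13.7) | 0% (0 to 11.6) |
| 3 | 12.0% (2.5 to 31.2) | 10.0% (2.1 to 26.5) |
| 5 | 20.0% (6.8 to 40.7) | 16.7% (5.6 to 34.7) |
| 8 | 32.0% (14.9 to 53.5) | 26.7% (12.3 to 45.9) |

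The chance of at least one extended course is 1 − (1 − p)^N. For assumed p of 5% and 10% it is 1 − 0.95^25 = 72% and 1 − 0.90^25 = 93% with 25 subjects, and 79% and 96% with 30. The row would probably not be empty even at modest rates.

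**3. Definition of extended use.** SAP Appendix A counts days as date2 − date1 + 1. With injection on Day 0, stopping at a Day 7 visit gives 7 − 0 + 1 = 8 days, and stopping at a Day 8 visit (allowed by the ±1 day window) gives 9. A literal cut at more than 7 days would flag subjects who merely stayed on drops until the visit.

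**4. Partial dates.** Appendix A sets a stop date with a missing day to month-end. A course from the 1st to the 7th of a 31-day month lasts 7 days, but becomes 31 − 1 + 1 = 31 days if the stop day is missing. Year-end imputation and the rule for wholly missing stop dates can add more.

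**5. Slit lamp coverage.** Protocol Table 2 and section 6.3.2 schedule the standard slit lamp and fundus exam at Day 1 and Day 28 but not at Day 7, when the steroid decision is made. Optional exploratory slit lamp imaging may occur at Day 7, but it is aimed at the cell aggregate and SAP 11.2 sends it to listings only.

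**The case against.** A reader might infer that eyes treated longer or more intensively look the same as uneventful eyes throughout the analysis. The documents do not support that. Inflammation reported as an adverse event appears by preferred term, highest severity and relationship (SAP 13.2). Flare is graded for each eye (13.3.1.1). The vitreous and macula exams are tabulated by eye and time point (13.3.1.2), as is IOP change (13.3.3), and macular edema is tabulated from OCT (13.3.5). A switch, which Protocol 5.3 foresees, gets its own row. An immunosuppressant other than topical steroid is prohibited, so its use would also be a listed deviation. With 25 to 30 subjects the medication listing can be read by eye.

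A second tempting reading is that any steroid use after Day 7 marks inflammation. It may be an ordinary taper, since the decision is left to the investigator and the documents describe the course in two ways.

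A third is that flare is the only inflammation-related slit lamp finding analyzed. Cataract type and grade are in the same section, slit lamp vitreous findings have listings, and diffuse haze is a category in the vitreous exam (13.3.4). Only anterior chamber cell is unnamed, and the eCRF and table shells are not available to show whether it is captured.

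These objections narrow the point but do not remove it. None of those outputs reports the steroid course, links an adverse event to the treatment given, or would show inflammation that was controlled by longer drops and never reported as an event. The adverse event tables have no study-eye split, and a listing is not a summary.

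**Conclusion.** The point holds in a limited form. For the one drug the protocol gives to everyone, the planned medication table reads about 100% whatever the course, so prolonged, restarted or intensified use of that drug appears in no planned table. Escalation to a different drug does appear, and other safety outputs give partial information about inflammation. The missing named row for anterior chamber cell is a smaller, separate gap between Protocol 7.1.5 and SAP 13.3.1.1.

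The conclusion assumes that subjects receive prednisolone as the protocol says and that its records code to one preferred name. The documents give no rate of extended use, so the size of the lost signal is unknown and the percentages above only illustrate what would become visible. This does not undermine the trial. It is an inexpensive improvement to the reporting of its primary objective, and it is best made before database lock, because SAP 6 labels later analyses post hoc.

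**What to change.** 1. Reconcile the steroid course in the protocol synopsis and SAP 4 with Protocol 5.3, so that a protocol period exists against which extension can be defined. This review does not favor either wording.

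2. Add one study-eye table of post-injection topical steroid, giving:
   - median and maximum days;
   - number and percentage still on it beyond the reconciled period (allowing for the Day 7 visit window), at Day 28 and at Month 3;
   - number and percentage with a restart, a switch or another route;
   - the documented reason, where captured.

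3. Compute durations from observed stop dates, or state a convention for partial ones. Do not use the month-end and year-end imputation, which SAP 9.5 already bars for durations.

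4. Add anterior chamber cell grade beside flare in Tables 14.3.3.1 and 14.3.3.2, where the eCRF captures it.

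Optional: split Table 14.1.5.1 into drugs started before injection and drugs started on or after it, and add a row for newly started IOP-lowering drugs. The gain there is smaller, because exclusion criterion 2 names elevated IOP and glaucoma and few such drugs should predate entry.

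The cost is SAP wording and one or two tables, with no new visits or procedures. Some stop dates may be partial. Protocol 5.3 asks for the reason to be documented but does not say it is on the eCRF, so that field and the treated eye need confirming first.
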